8.3.2 Serious Adverse Event

An adverse event is considered “serious” if, in the view of either the investigator or sponsor-investigator, it results in any of the following outcomes:

- Death
If death results from (progression of) the disease, the disease should be reported as event (SAE) itself.
- A life-threatening adverse event
An adverse even is considered ‘life-threatening’ if, in the view of either the investigator [or sponsor-investigator], its occurrence places the patient or subject at immediate risk of death. It does not include an adverse event that, had it occurred in a more severe form, might have caused death.
- Inpatient hospitalization or prolongation of existing hospitalization for ≥ 24 hours.
- A persistent or significant incapacity or substantial disruption of the ability to conduct normal life functions
- A congenital anomaly/birth defect
- Important medical event
Any event that may not result in death, be life-threatening, or require hospitalization may be considered serious when, based upon appropriate medical judgment, they may jeopardize the patient and may require medical or surgical intervention to prevent one of the outcomes listed in this definition of “Serious Adverse Event”. Examples of such medical events include allergic bronchospasm requiring intensive treatment in an emergency room or at home; convulsions that do not result in inpatient hospitalization or the development of drug dependency or drug abuse.

Previously planned (prior to signing the informed consent form) surgeries should not be reported as SAEs unless the underlying medical condition has worsened during the course of the study. Preplanned hospitalizations or procedures for preexisting conditions that are already recorded in the patient's medical history at the time of study enrollment should not be considered SAEs. Hospitalization or prolongation of hospitalization without a precipitating clinical AE (for example, for the administration of study therapy or other protocol-required procedure) should not be considered SAEs. However, if the preexisting condition worsened during the course of the study, it should be reported as an SAE.

8.3.3 Expected Adverse Events

An adverse event (AE) is considered "expected" if:

- For approved and marketed drugs or devices, those adverse events are described in the approved Package Insert (Label).
- For investigational new drugs or devices, those adverse events are described in the FDA Investigator's Brochure.
- In clinical research studies, information on expected adverse events is also summarized in the protocol and in the consent document. See section 9.1 for the list of expected adverse events related to the drug under study.

8.3.4 Unexpected Adverse Event

An adverse event (AE) is considered "unexpected" if it is not described in the Package Insert, Investigator's Brochure, in published medical literature, in the protocol, or in the informed consent document.

8.4 Adverse Event Characteristics

8.4.1 CTCAE Term

(AE description) and grade: The descriptions and grading scales found in the NCI Common Terminology Criteria for Adverse Events (CTCAE) version 4.03 will be utilized for AE reporting. All appropriate treatment areas should have access to a copy of the CTCAE version 4.03. A copy of the CTCAE version 4.03 can be down loaded from the CTEP web site. (<http://ctep.cancer.gov>)

8.4.2 Attribution of the AE

The investigator or co-investigator is responsible for assignment of attribution.

Definite – The AE is *clearly related* to the study treatment.

Probable – The AE is *likely related* to the study treatment.

Possible – The AE *may be related* to the study treatment.

Unlikely – The AE is *doubtfully related* to the study treatment.

Unrelated – The AE is *clearly NOT related* to the study treatment.

8.5 Serious Adverse Event Reporting Guidelines

All SAEs and UPs must be reported to the Coordinating Center within 24 hours of first awareness of the event. Events should be reported using the Coordinating Center SAE form. A copy of the Coordinating Center SAE form should be sent to the Coordinating Center via fax at [contact] or via email to [contact] within 24 hours of the site's knowledge of the event.

Contact information for Principal Investigator SAE Reporting:

[name].
University of Michigan Rogel Cancer Center
[name]
[name]
[contact], [contact]
[contact]

Follow-up information must also be reported within 24 hours of receipt of the information by the investigator.

All SAEs and UPs will be reported to the local IRBs per current institutional standards.

The Coordinating Center will disseminate information regarding SAEs and UPs to the participating sites within 5 days of review of the information by the Coordinating Center's Principal Investigator (or designee in the event of extended absence) only in the case that the event(s) is believed to be related (i.e., possibly, probably, or definitely) to the study drug.

The Coordinating Center will be responsible for reporting to Pfizer by facsimile any Serious Adverse Event that occur during the SAE reporting period. The coordinating center will report the SAE within 24 hours of first awareness of the event (immediately if the event is fatal or life-threatening).

The Multi-site team will coordinate with the Sponsor-Investigator and the Michigan Institute for Clinical and Health Research (MICHR) IND/IDE Investigator Assistance Program (MIAP) office for the reporting of any and all IND safety reports to the FDA as per the requirements outlined in 21 CFR 312.32. A summary of all non-expedited safety reports will be submitted in the annual report.

In addition to new events, any increase in the frequency or severity (i.e., toxicity grade) of a pre-existing condition that occurs after the patient begins study treatment is also considered an adverse event.

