8.7 Reporting of Unanticipated Problems

There are types of incidents, experiences and outcomes that occur during the conduct of human subjects research that represent unanticipated problems but are not considered adverse events. For example, some unanticipated problems involve social or economic harm instead of the physical or psychological harm associated with adverse events. In other cases, unanticipated problems place subjects or others at increased risk of harm, but no harm occurs.

Upon becoming aware of any incident, experience, or outcome (not related to an adverse event) that may represent an unanticipated problem, the investigator should assess whether the incident, experience, or outcome represents an unanticipated problem. The incident, experience or outcomes is considered unanticipated if it meets all of the following criteria:

1. Unexpected (in terms of nature, severity, or frequency);
2. Related or possibly related to participation in the research; and

3. Suggests that the research places subjects or others at a greater risk of harm than was previously known or recognized.

If the investigator determines that the incident, experience, or outcome represents an unanticipated problem, the investigator must report it to the IRB according to the local IRB reporting requirements.

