10.1.2 Tumor Samples

10.1.2.1 We plan on obtaining tumor samples at screening, at Cycle 2 Day 1, and at progression.

- Screening biopsy sample is mandatory. This must be obtained within the 56 days prior to study treatment. No systemic therapy (i.e. immunotherapy) may have been administered since obtaining the biopsy, if so, a new biopsy is needed.
- Interim Biopsy at Cycle 2, Day 1 (+/- 7 days) is optional and will be offered if safe and clinically feasible
- Biopsy at the time of progression is mandatory however if the treating physician deems biopsy to be either unsafe or not clinically feasible, this must be documented and patient may forego repeat biopsy
- FFPE core biopsy is preferred, However, if not clinically feasible or safe to obtain a core biopsy, contact coordinating site PIs ([name]) as a block made from several FNA passes is acceptable.

[figure not shown]

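### Section 8.5 tells the other sites only about drug-related SAEs and UPs, so a UP or SAE that arises from the research but not from the drug has no stated route to them

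*Combined protocol and SAP*

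**What the plan says.** Section 8.5 requires sites to report all SAEs and UPs to the Coordinating Center within 24 hours of awareness. For the return direction it states: "The Coordinating Center will disseminate information regarding SAEs and UPs to the participating sites within 5 days of review of the information". That duty then carries a condition. It applies, after review by the Coordinating Center's Principal Investigator or designee, "only in the case that the event(s) is believed to be related (i.e., possibly, probably, or definitely) to the study drug". One condition covers SAEs and UPs together.

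Section 8.7 deals with incidents that "represent unanticipated problems but are not considered adverse events". Such an incident must meet three criteria, all of them: it is unexpected; it is "Related or possibly related to participation in the research; and" it meets the third, "Suggests that the research places subjects or others at a greater risk of harm than was previously known or recognized". The only recipient that 8.7 names is the IRB.

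Section 8.4.2 supplies the causality grades. They are worded for adverse events and for relation to study treatment, and "The investigator or co-investigator is responsible for assignment of attribution".

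**The concern.** The test for telling the other sites is not the test that makes something a UP. Section 8.5 asks about the drug. Section 8.7 asks about the research and about newly recognised risk. An event can satisfy every criterion in 8.7 and still fail the condition in 8.5.

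What is at stake is patient safety at the other sites. By its third criterion, a UP is evidence that subjects or others are at more risk than was thought. If the cause is a study procedure, or the way consent or data are handled, the other sites are likely to be doing the same thing. Under the rule as written they could go on enrolling and treating without hearing of it, while the Coordinating Center already holds the report.

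The same condition also holds back an SAE that a protocol-required procedure caused and the drug did not. Section 10.1.2 plans an optional interim biopsy around Cycle 2 Day 1, and a biopsy at progression that is mandatory unless it is documented as unsafe or not feasible. Other sites performing those biopsies would have an interest in a serious complication.

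**Working it through.** No arithmetic in the plan bears on this point. The check is to follow each kind of event through the reporting text.

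**Step 1: what goes in.** Section 8.2 (Adverse Event Reporting Requirements) sends all SAEs and UPs to the Principal Investigator and the Coordinating Center whatever their causal link to the drug. Section 8.5 sets the 24-hour limit. Collection upward is complete.

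**Step 2: what comes back out.** Only Section 8.5 describes a return flow to the sites, and it is limited to drug-related events. Section 8.7 names the IRB. Section 12.0 describes quarterly reports and deviation notices (within 7 calendar days) going from the sites to the Coordinating Center, with no flow back.

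**Step 3: apply the rule to each type of event.**

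| Event | Reaches the Coordinating Center | Sent to sites under 8.5 |
|---|---|---|
| UP believed related to the drug | Yes | Yes |
| UP related to the research but not the drug (procedure, privacy, consent) | Yes | No stated route |
| SAE at least possibly related to the drug | Yes | Yes |
| SAE in the collection window, caused by the interim or progression biopsy and not the drug | Yes | No stated route |

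The collection window in Section 8.2 runs from the first study treatment to 30 days after the last dose. The interim biopsy falls inside it. A progression biopsy does too if it is done within those 30 days.

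**Step 4: how many sites could go without notice.** The synopsis allows up to 3 sites, including the lead site. If the event arises at the lead site, 3 − 1 = 2 others could be uninformed. If it arises elsewhere, and notice to the Coordinating Center is taken to inform the lead site because both belong to the same institution, 3 − 1 − 1 = 1. Both figures are maxima per event.

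The documents give no rate for non-drug UPs or for biopsy complications, so the number of affected events cannot be calculated.

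**The case against.** A reader might go further and infer that no UP of the 8.7 kind can ever reach the other sites, because such UPs are not adverse events and the causality grades are written for adverse events. The documents do not support that. Section 8.7 concerns "any incident, experience, or outcome (not related to an adverse event) that may represent an unanticipated problem"; being unrelated to an adverse event is not the same as being unrelated to the drug. A drug-supply problem that raised risk without causing harm (an assumed example) could meet 8.7 and also satisfy 8.5. Section 8.5 names UPs expressly and asks for a belief about relatedness after the Principal Investigator's review, so it does not depend on an 8.4.2 grade. Nor does 8.7 say that all UPs lie outside the adverse events; it addresses the type that does.

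A reader might also gauge the size of the problem by counting biopsies. That fails too. A count of procedures is not a count of events. And although "Screening biopsy sample is mandatory", a complication that begins before the first dose is treated as pre-existing under Section 8.2 and is not collected as an SAE, so the 8.5 condition does not withhold it as one.

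The best defence of the plan is that oversight exists: the Coordinating Center and the Principal Investigator see everything, local IRBs receive all SAEs and UPs, and a Data and Safety Monitoring Committee monitors safety. One could add that the condition limits only the five-day duty and leaves the Coordinating Center free to tell sites more. This lowers the risk, since a body able to act is informed. It does not supply a written route to the other sites, and the wording points away from one.

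It can also be said that circulating every UP would spread one subject's social or economic harm without purpose. That has some force, and it is why the change should be confined to events confirmed against all three criteria in 8.7, including the one on greater risk.

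**Conclusion.** The point holds in a limited form. Sections 8.5 and 8.7 use different tests. As a result, UPs related to the research but not to the drug, and SAEs in the collection window caused by a required procedure and not by the drug, have no stated route to the other sites. UPs believed to be drug-related do have one.

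At most two sites would be uninformed per event. The number of events is likely to be small, though that is a judgement and not a figure from the documents. The conclusion assumes that the Coordinating Center follows 8.5 as written and that no separate procedure outside these documents provides the notice. The two-stage design, the endpoints and the analysis are unaffected. It is a patient-safety correction worth making, because the gap is in a stated rule and is easily closed.

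**What to change.** Reword the dissemination sentence in Section 8.5. Within 5 days of review, the Coordinating Center sends the participating sites:

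- (a) every event confirmed as a UP under the criteria in Section 8.7, whatever its relation to the drug; and
- (b) every SAE judged at least possibly related to study treatment or to a protocol-required procedure.

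A cross-reference from 8.7 to the revised sentence would keep the two sections aligned. The cost is one sentence and a few more notices to the sites. The Coordinating Center already receives all of these reports, so sites have no new reports to submit. It would need to note, at review, whether a procedure may have caused the SAE, since the grades in 8.4.2 cover study treatment only.

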8.6 Routine Reporting

All other adverse events- such as those that are expected, or are unlikely or definitely not related to the study participation- are to be reported annually as part of regular data submission.

8.7 Reporting of Unanticipated Problems

There are types of incidents, experiences and outcomes that occur during the conduct of human subjects research that represent unanticipated problems but are not considered adverse events. For example, some unanticipated problems involve social or economic harm instead of the physical or psychological harm associated with adverse events. In other cases, unanticipated problems place subjects or others at increased risk of harm, but no harm occurs.

Upon becoming aware of any incident, experience, or outcome (not related to an adverse event) that may represent an unanticipated problem, the investigator should assess whether the incident, experience, or outcome represents an unanticipated problem. The incident, experience or outcomes is considered unanticipated if it meets all of the following criteria:

1. Unexpected (in terms of nature, severity, or frequency);
2. Related or possibly related to participation in the research; and

3. Suggests that the research places subjects or others at a greater risk of harm than was previously known or recognized.

If the investigator determines that the incident, experience, or outcome represents an unanticipated problem, the investigator must report it to the IRB according to the local IRB reporting requirements.

9.0 DRUG INFORMATION

9.1 Carboplatin

- Other names for the drug: Carboplatin (Paraplatin ®)
- Description: IV Medication. Vial sizes of 50 mg/5 mL, 150 mg/15 mL, 450 mg/45 mL, 600 mg/60 mL all in individually packaged multi-dose vials.
- Classification - type of agent: Cytotoxic/Alkylating-Like Compound
- Mode of action: Carboplatin produces interstrand DNA cross-links which in turn interfere with mitosis. DNA damage leads to attempts at DNA repair however, when repair is not possible apoptosis is activated, especially in the case of double strand DNA breaks.
- Pharmacokinetics: Carboplatin exhibits linear pharmacokinetics with Cmax and AUC increasing linearly with dose.
 - Half-life- Plasma levels of intact carboplatin decay in a biphasic manner with a half-life of 2.6-5.9 hours.
 - Elimination- The major route of elimination is renal excretion. The primary determinant of carboplatin clearance is glomerular filtration rate
 - Metabolism- Minimally hepatic to aquated and hydroxylated compounds
- Side effects:
 - The most common adverse reactions (incidence \geq 10%) are bone marrow suppression (anemia, thrombocytopenia, and/or neutropenia), nausea, vomiting, mild elevations in alkaline phosphatase, and mild decreases in serum electrolyte values
 - Hypersensitivity to carboplatin has been reported in 2% of patients. These allergic reactions have been similar in nature and severity to those reported with other platinum containing compounds and have been successfully managed with standard epinephrine, corticosteroid, and antihistamine therapy
 - Please refer to the package insert for a comprehensive list of adverse events.
- Drug Interactions:
 - Fosphenytoin/Phenytoin- Carboplatin may decrease serum concentrations of these drugs hence monitor therapy
- Storage and stability:
 - Unopened vials of carboplatin are stable to the expiration date indicated on the

package when stored at 25°C (77°F); excursions permitted from 15°C-30°C (59°-86°F). Protect from light

- Multidose vials maintain microbial, chemical, and physical stability for up to 14 days at 25°C following multiple needle entries
- Parenteral drug products should be visually inspected for particulate matter and discoloration prior to administration. Solutions for infusion should be discarded 8 hours after preparation
- Administration:
 - Needles or intravenous administration sets containing aluminum parts that may come in contact with carboplatin should not be used for the preparation or administration of the drug as aluminum can react with carboplatin causing precipitate formation and loss of potency
- Availability: Commercially available. Will be purchased from commercial sources and billed to patients or their insurers

9.2 Palbociclib

- Other names for the drug: Palbociclib (Ibrance ®)
- Description: Oral Medication. Supplied as capsules which must be swallowed or solution which may be swallowed or administered via feeding tube (ie nasogastric tube or PEG). Capsules are supplied in 125 mg, 100 mg, 75 mg doses. Bottles consist of 21 tablets. Solution is supplied at a concentration of 25 mg/mL and 112 mL are in each bottle
- Classification - type of agent: Cyclin-dependent kinase (CDK) 4 and 6 inhibitor
- Mode of action: Palbociclib is an inhibitor of CDK 4/6. Cyclin D1, CDK 4, and CKD 6 are downstream signaling pathways which lead to cellular proliferation. In vitro, palbociclib reduced cellular proliferation of estrogen receptor-positive breast cancer cell lines by blocking the progression of the cell from G1 into S phase of the cell cycle.
- Pharmacokinetics:
 - Absorption- The mean time to reach maximum concentration (Tmax) is between 6-12 hours following oral administration. The mean bioavailability of palbociclib after an oral 125 mg dose is 46% and in the dosing range of 25-225 mg the AUC and Cmax increased proportionally with dose in general. Steady state was achieved within 8 days following repeated once daily dosing. In studies utilizing capsules, food intake reduced the intersubject variability of palbociclib exposure therefore the palbociclib capsules should be taken with food. Pharmacokinetic studies of the solution demonstrate no change in the variability of palbociclib exposure with food administration. Therefore, palbociclib solution may be taken with or without food.
 - Half-life- The plasma elimination half-life is 29 (+/- 5) hours in patients with advanced breast cancer
 - Metabolism- Palbociclib undergoes hepatic metabolism in humans. The primary metabolic pathways for palbociclib involve oxidation and sulfonation. CYP3A and

SULT2A1 are mainly involved in the metabolism of palbociclib. Palbociclib is a weak time-dependent inhibitor of CYP3A following daily dosing to steady state.

- Elimination- Fecal elimination is the major route of excretion (74.1%) with an additional 17.5% recovered in urine. The majority of excreted materials were metabolites
- Side effects:
 - The most common adverse reactions (incidence \geq 10%) are neutropenia, leukopenia, infections, fatigue, nausea, anemia, stomatitis, headache, diarrhea, thrombocytopenia, constipation, alopecia, vomiting, rash, and decreased appetite
- Drug Interactions:
 - None applicable
- Storage and stability:
 - Store at 20° C -25° C (68° F-77° F), excursions permitted between 15° C-30° C (59° F-86° F)
 - Palbociclib must be stored in a secure, limited access area.
- Preparation and Dispensing:
 - **How Supplied:** Supplied as capsules which must be swallowed or solution which may be swallowed or administered enterally via feeding tubes (ie nasogastric tube or gastric tube).
 - Capsules are supplied in 125 mg, 100 mg, 75 mg doses. Bottles consist of 21 tablets.
 - Oral solution is supplied at a concentration of 25 mg/mL and 112 mL are in each bottle Oral solution (25 mg/mL) will be supplied in HDPE packaged bottles with a PIBA (push in bottle adapter) and a reusable oral syringe for dosing. Labeling will occur according to local regulatory requirements. Each clinical site will be provided the oral solution product manual which contains the detailed dosage and administration instructions for preparation of the oral solution. Please note the oral solution product manual is sponsor-provided and utilized for multiple studies. All references to placebo formulation do not apply for this protocol and should be disregarded.
 - **Note:** Capsules should not be repackaged after they are dispensed. Capsules should not be opened or emptied into another vehicle for oral delivery. Similarly, oral solution should not be transferred into any other container.
- Administration:
 - Palbociclib Capsules
 - Take once daily by mouth at approximately the same time each day.
 - Palbociclib should be taken orally with food
 - Patients should be instructed that if they vomit any time after taking a dose, that they must not “make it up” with an extra dose, but instead resume subsequent doses as prescribed. Missed doses may be taken late, up to 6 hours after the scheduled dose, otherwise should be skipped and reported to the investigators.
 - Palbociclib Solution
 - Will be available for patients who are unable to swallow capsules or develop

an inability to swallow capsules during the study.

- Will be administered using an oral syringe at volumes corresponding to the dose prescribed by the investigator (125 mg dose = 5mL, 100 mg dose = 4 mL, and 75 gm dose = 3 mL). Detailed instructions patient administration directions using syringe are detailed in Pfizer Approved 'Administration Instruction' Handouts (Appendix C- Administration Instructions for Oral Dose Using Syringe and Appendix D- Administration Instructions for Each Dose via NG Tubes)
- Take once daily at approximately the same time each day
- Solution does not need to be taken with food
- May be taken by mouth or by administration via feeding tube
- The patients will be asked to bring medication bottles to each follow-up visit, and remaining pills in bottle will be counted at each visit to document compliance. This information will be recorded in each patient's data file.
- If patients are being treated with oral solution, they will be asked to return the bottles in clear ziplock bag. For drug accountability research staff may use a best approximation as to the remaining solution as they may be unable to open HDPE bottles.
- Drug administration will be provided by the Coordinating Center to record compliance with study drug administration, route of administration (by mouth or feeding tube) as well as document dose adjustments.
- Availability: Provided by sponsor free of charge.
 - Under no circumstance will the study medication palbociclib be used other than as directed by the protocol.
 - Do Not Use Commercially Available Product.
- Drug Accountability:
The investigator, or a responsible party designated by the investigator, must maintain a careful record of the inventory and disposition of the drug, palbociclib. The drug accountability records will capture drug receipt, drug dispensing, drug return and final disposition.

